#### 6.2 **Pembrolizumab**

AEs associated with pembrolizumab exposure, including coadministration with additional compounds, may represent an immunologic etiology. These immune-related AEs (irAEs) may occur shortly after the first dose or several months after the last dose of pembrolizumab/combination treatment and may affect more than one body system simultaneously. Therefore, early recognition and initiation of treatment is critical to reduce complications. Based on existing clinical study data, most irAEs were reversible and could be managed with interruptions of pembrolizumab/combination treatment, administration of corticosteroids and/or other supportive care. For suspected irAEs, ensure adequate evaluation to confirm etiology or exclude other causes. Additional procedures or tests such as bronchoscopy, endoscopy, skin biopsy may be included as part of the evaluation. Based on the severity of

### Attribution of Toxicity:

When study interventions are administered in combination, attribution of an adverse event to a single component is likely to be difficult. Therefore, while the investigator may attribute a toxicity event to the combination, to mirvetuximab soravtansine alone or to pembrolizumab alone, for adverse events listed in Table 7, both interventions must be held according to the criteria in Table 7 Dose Modification Guidelines for Pembrolizumab.

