#### DOSING DELAYS/DOSE MODIFICATIONS

Every effort should be made to administer study treatment on the planned dose and schedule.

Dose delays and modifications will be made as indicated in the following table(s). The descriptions and grading scales found in the revised NCI Common Terminology Criteria for Adverse Events (CTCAE) version 5.0 will be utilized for dose delays and dose modifications. A copy of the CTCAE version 5.0 can be downloaded from the CTEP website http://ctep.cancer.gov/protocolDevelopment/electronic\_applications/ctc.htm.

Patients experiencing AEs that can be clearly attributed to mirvetuximab soravtansine or pembrolizumab will have the corresponding agent modified or withheld. In case of an AE recurrence, the other drug in the combination regimen will then be modified or withheld. If a relationship of an AE to a particular drug cannot be clearly determined, the order in which the drugs are to be reduced will require approval from the Overall PI.

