### **Restarting Study Interventions:**

Participants may not have any dose modifications (no change in dose or schedule) of pembrolizumab in this study, as described in Table 7.

- If the toxicity does not resolve or the criteria for resuming treatment are not met, the participant must be discontinued from all study interventions.
- If the toxicities do not resolve and conditions are aligned with what is defined in Table 7, the combination of mirvetuximab soravtansine and pembrolizumab bay be restarted at the discretion of the investigator. In these cases where the toxicity if attributed to the combination or to mirvetuximab soravtansine alone, re-initiation of pembrolizumab as a monotherapy may be considered at the PI's discretion.

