#### 6.3 **Re-treatment Criteria**

For a patient to begin a new cycle or continue a cycle of therapy after a dose modification, the following criteria must be met.

- Pre-treatment criteria as described in Section 5.2.2 with the following exceptions
  - $\circ$  Treatment-emergent ocular disorders, which must have recovered to  $\leq$  Grade 1 or baseline
  - $\circ$  Treatment-emergent pneumonitis which must have recovered to  $\leq$  Grade 1

If the patient does not meet these criteria, dosing with the two agents in the combination regimen will be delayed and the patient should be re-evaluated within 48-72 hours. Dosing with both agents may resume if these criteria have been met. If the adverse event can be attributed to one of the agents in the combination regimen, that agent will be held or discontinued as per the Dose Modification Guidelines

described in Sections 6.1 and 6.2 respectively; however, treatment with the second agent may resume provided all the other criteria are met. However, if the next cycle is delayed due to treatment-related toxicity longer than 12 weeks then the patient should be removed from study treatment. In such cases, continuation of study treatment may be considered for those patients who have experienced clinical benefit if agreed upon between the Overall PI and the Investigator.

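### For Table 7 events other than pneumonitis, Section 6.2 holds both drugs whatever the attribution, Sections 6 and 6.3 release the unblamed drug, and one restart rule in 6.2 is worded backwards

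*Combined protocol and SAP*

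**What the plan says.** All the rules are in Section 6 of the combined protocol and SAP.

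- **Section 6, opening.** "Patients experiencing AEs that can be clearly attributed to mirvetuximab soravtansine or pembrolizumab will have the corresponding agent modified or withheld". The other drug comes into play only later: "In case of an AE recurrence, the other drug in the combination regimen will then be modified or withheld".
- **Section 6.2, Attribution of Toxicity.** Even if the investigator attributes an event to one drug alone, "for adverse events listed in Table 7, both interventions must be held according to the criteria in Table 7". The paragraph on holding study interventions repeats the two-drug hold for any event judged immune-related.
- **Section 6.2, Restarting Study Interventions, first bullet.** "If the toxicity does not resolve or the criteria for resuming treatment are not met, the participant must be discontinued from all study interventions".
- **Same place, second bullet.** It opens "If the toxicities do not resolve and conditions are aligned with what is defined in Table 7" and then allows the combination to be restarted. For toxicity blamed on mirvetuximab or on the combination, it adds that "re-initiation of pembrolizumab as a monotherapy may be considered". It says nothing about mirvetuximab alone.
- **Section 6.3.** Both drugs are first delayed if the re-treatment criteria are not met. Then: "If the adverse event can be attributed to one of the agents in the combination regimen, that agent will be held or discontinued", following Sections 6.1 and 6.2, while "treatment with the second agent may resume provided all the other criteria are met". Special recovery limits are given for ocular disorders and pneumonitis, but not for Table 7 events.

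Table 7 states its actions, and its 12-week stopping rule, for pembrolizumab only. Table 4 (pneumonitis) names both drugs, so pneumonitis is outside this point. So are the Table 7 rows where dosing continues (Grade 2 hyperthyroidism and Grade 2 to 4 hypothyroidism).

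**The concern.** A site that follows the opening of Section 6, or Section 6.3, as written can give mirvetuximab, a cytotoxic conjugate, during an immune-related event for which Section 6.2 requires both drugs to be held. After a permanent pembrolizumab stop, one site could end all treatment under 6.2 and another could continue mirvetuximab under 6.3 for the same event, each able to cite the protocol. Several centers take part, so uneven handling is foreseeable. At stake are patient safety and consistent mirvetuximab exposure. The paragraph that a site would consult to settle the question is also the one that contains the reversed restart condition.

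**Working it through.** The plan gives no figure to reproduce on this point. The check sets the rules side by side for an event attributed to pembrolizumab alone.

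**Initial hold: what happens to mirvetuximab**

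| Event (Table 7 action) | Section 6.2 | Section 6 opening, first event | Table 5, if applied whatever the attribution |
|---|---|---|---|
| Grade 1 myocarditis (withhold) | held | not held | no dose change |
| Suspected SJS/TEN/DRESS (withhold) | held | not held | depends on a grade that Table 7 does not give |
| Grade 2 hepatic, renal or pituitary event (withhold) | held | not held | held until Grade 1 or less |
| Grade 3 AST/ALT elevation (permanent stop) | held | not held | held, then resumed one level lower |

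In the last two rows Table 5, read that way, gives the same initial hold as 6.2. In the first row it does not. Section 6.3 does not help there either: it relies on the Section 5.2.2 limit of Grade 2 or less for earlier toxicity, which a Grade 1 event already meets. Grade 1 myocarditis is therefore the clearest case.

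**The restart bullets.** The first bullet stops everything when toxicity has not resolved. The second, read literally, allows a restart in the same situation. Both cannot hold. The second makes sense only if the condition is that toxicities *do* resolve.

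**Permanent pembrolizumab stop.** Take a Grade 3 AST/ALT elevation attributed to pembrolizumab.

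1. Table 7 ends pembrolizumab for good.
2. If the resumption criteria in the first restart bullet are those for pembrolizumab, they can never be met, and the bullet ends mirvetuximab too.
3. Section 6.3 covers a drug that has been discontinued and lets the other resume once the remaining criteria are met. Table 5 foresees a return one dose level lower after Grade 3.
4. Other text does not decide it. Sections 5.1 and 5.5 mention mirvetuximab alone only after 35 cycles.
5. At Grade 4 the question largely disappears, because Table 5 takes the participant off protocol therapy.

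**Illustration only.** Taking six months as 182 days, dosing every 21 days gives dates on days 1, 22, ..., 169, since 1 + 21 × 8 = 169: 9 dates. If pembrolizumab stops for good after dose 2, 9 − 2 = 7 dates remain. The stop-everything reading loses all 7. Section 6.3 loses none if the participant has recovered by day 43. This shows how far apart two sites could be for one such patient. The documents do not give the number of patients affected.

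**The case against.** The strongest reply is that this is a general rule with a specific exception. Section 6.2 takes up attribution directly, says that attributing an event to one component is likely to be difficult, and still requires both drugs to be held. Section 6 applies only to clear attribution and points to the tables that follow. Section 6.3 first delays both drugs and refers back to Sections 6.1 and 6.2. Much of this stands: 6.2 probably governs the initial hold. The opening paragraph of 6.2 is also cut off in the text available, so one cannot say that the full protocol is silent on precedence. But the cross-reference in 6.3 governs how the blamed drug is handled, and the clause after it releases the other drug.

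On a permanent stop, the texts can be read in sequence: hold both, stop all if the toxicity persists, and let mirvetuximab resume if it clears. The first bullet speaks of resuming treatment, not of resuming pembrolizumab. Table 7 names only pembrolizumab where Table 4 names both, which also favors mirvetuximab continuing. That is a fair reading, but the text does not compel it.

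Three stronger readings are tempting but unsupported.

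- *Every hold-grade row of Table 7 conflicts on the initial hold.* Table 5, if it applies to unblamed events, already holds mirvetuximab at Grades 2 and 3.
- *The doses lost can be bounded.* A 12-week delay passes 84 / 21 = 4 dosing dates, which suggests a ceiling of 4 under Section 6.3 and a gap of 7 − 4 = 3 to 7 − 0 = 7 dates in the illustration. But 6.3 allows continuation after a longer delay for patients with clinical benefit, if the Overall PI and the investigator agree. A loss of zero under Section 6 likewise holds only where Table 5 does not itself hold mirvetuximab.
- *The protocol means to allow restart with unresolved toxicity.* The first bullet says the opposite, so a stray negative is the likelier explanation.

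**Conclusion.** The concern holds in a limited form: operative safety rules are wrong as written, with minor to moderate consequences. Sections 6 and 6.3 lack the exception that 6.2 needs. The practical conflict on the initial hold is clearest for Grade 1 myocarditis attributed to pembrolizumab and for suspected SJS/TEN/DRESS. The second restart bullet contradicts the first. For permanent pembrolizumab stops below Grade 4, the first bullet and Section 6.3 can lead to opposite decisions about mirvetuximab.

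This rests on the legible text, and the narrowing to those two cases assumes that Table 5 applies whatever the attribution. If it applies only to events blamed on mirvetuximab, the conflict on the initial hold is wider. No reliable bound on doses lost, and no count of patients affected, can be drawn from the documents. Sample size, alpha and power are unaffected.

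**What to change.** 1. In the opening of Section 6 and in Section 6.3, add: *except for Table 7 events at grades requiring a hold, for which both agents are held per Section 6.2*. Writing *grades or conditions* would also cover the ungraded rows.
2. In Section 6.2, Restarting Study Interventions, begin the second bullet: *If the toxicities do resolve*.
3. In the same amendment, align the first restart bullet with Section 6.3 on whether mirvetuximab alone may continue after a permanent pembrolizumab stop below Grade 4. Which way to go is a clinical decision for the sponsor. This third step completes a missing detail; the first two correct text that is wrong.

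The cost is amendment wording in three places and one clinical decision, with no new visits, procedures or patients. The downside is that some participants may miss a few mirvetuximab doses that the opening of Section 6 would have allowed.

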### **Holding Study Interventions:**

When study interventions are administered in combination, if the AE is considered immunerelated, both interventions should be held according to recommended dose modifications.

### **Restarting Study Interventions:**

Participants may not have any dose modifications (no change in dose or schedule) of pembrolizumab in this study, as described in Table 7.

- If the toxicity does not resolve or the criteria for resuming treatment are not met, the participant must be discontinued from all study interventions.
- If the toxicities do not resolve and conditions are aligned with what is defined in Table 7, the combination of mirvetuximab soravtansine and pembrolizumab bay be restarted at the discretion of the investigator. In these cases where the toxicity if attributed to the combination or to mirvetuximab soravtansine alone, re-initiation of pembrolizumab as a monotherapy may be considered at the PI's discretion.

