## **Table 4: Management of Pneumonitis**

	CTCAE v5.0 Severity	Dose Modifications	irAE management	Monitor and follow-
--	---------------------	---------------------------	-----------------	---------------------

Grade		with corticosteroid and/or other therapies	up
Grade 1	Continue dosing after discussion with the Overall PI		
Grade 2	Withhold mirvetuximab soravtansine and pembrolizumab (both agents) Mirvetuximab soravtansine can be resumed at a dose reduced by one dosing level (see Table 6), and pembrolizumab can be resumed at same dosing level after discussion with the Overall PI when symptoms resolve to ≤ Grade 1	Administer corticosteroids (initial dose of 1-2 mg/kg prednisone or equivalent) followed by taper*	
 
Monitor participants for signs and symptoms of pneumonitis
 
Evaluate participants with suspected pneumonitis with radiographic imaging and initiate corticosteroid treatment
 
Add prophylactic antibiotics for opportunistic infections
 

Grade 3 or 4, or recurrent Grade 2	Permanently discontinue mirvetuximab soravtansine and pembrolizumab (both agents)	Administer corticosteroids (initial dose of 1-2 mg/kg prednisone or equivalent) followed by taper*	
 
Monitor participants for signs and symptoms of pneumonitis
 
Evaluate participants with suspected pneumonitis with radiographic imaging and initiate corticosteroid treatment
 
Add prophylactic antibiotics for opportunistic infections
 

\* Notes on steroids for irAE:

1. Corticosteroid taper should be initiated upon AE improving to Grade 1 or less and continue to taper over at least 4 weeks.

 Pembrolizumab and mirvetuximab soravtansine can be resumed after AE has been reduced to Grade 1 or 0 and corticosteroid has been tapered. Both agents should be permanently discontinued if AE does not resolve within 12 weeks of last dose or corticosteroids cannot be reduced to ≤10 mg prednisone or equivalent per day within 12 weeks.

**3.** For severe and life-threatening irAEs, IV corticosteroid should be initiated first followed by oral steroid. Other immunosuppressive treatment should be initiated if irAEs cannot be controlled by corticosteroids.

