## Table 7: Dose Modification Guidelines for Pembrolizumab

#### Instructions:

- 1. Corticosteroid taper should be initiated upon AE improving to Grade 1 or less and continue to taper over at least 4 weeks.
- 2. For situations where pembrolizumab has been withheld, pembrolizumab can be resumed after AE has been reduced to Grade 1 or 0 and corticosteroid has been tapered. Pembrolizumab should be permanently discontinued if AE does not resolve within 12 weeks of last dose or corticosteroids cannot be reduced to ≤10 mg prednisone or equivalent per day within 12 weeks.
- **3.** For severe and life-threatening irAEs, IV corticosteroid should be initiated first followed by oral steroid. Other immunosuppressive treatment should be initiated if irAEs cannot be controlled by corticosteroids.

Immune-related AEs	Toxicity grade or conditions (CTCAEv5.0)	Action taken to pembrolizumab	irAE management with corticosteroid and/or other therapies	Monitor and follow-up
Pneumonitis	See Table 4	See Table 4	See Table 4	See Table 4

NCI Protocol #: N/A DF/HCC Protocol #: 18-602 rsion Date: December 11, 2023

			Protocol	Version Date: December 11, 2
Diarrhea / Colitis	Grade 2 or 3 Withhold	
 
Administer corticosteroids (initial dose of 1- 2 mg/kg prednisone or equivalent) followed by
 
	Monitor     participants for     signs and     symptoms of     enterocolitis (ie,     diarrhea,     abdominal pain,	
		discontinue	taper	
 
blood or mucus in stool with or without fever) and of bowel perforation (ie, peritoneal signs and ileus).
 
Participants with ≥ Grade 2 diarrhea suspecting colitis should consider GI consultation and performing endoscopy to rule out colitis.
 
Participants with diarrhea/colitis should be advised to drink liberal quantities of clear fluids. If sufficient oral fluid intake is not feasible, fluid and electrolytes should be substituted via IV infusion.
 

AST / ALT elevation or Increased bilirubin	Grade 2	Withhold	Administer corticosteroids (initial dose of 0.5-1 mg/kg prednisone or equivalent) followed by taper	Monitor with liver function tests (consider weekly or more frequently until liver enzyme value returned to baseline or is
	Grade 3 or 4	Permanently discontinue	• Administer corticosteroids (initial dose of 1- 2 mg/kg prednisone or equivalent)	stable

NCI Protocol #: N/A DF/HCC Protocol #: 18-602 Protocol Version Date: December 11, 2023

			followed by taper	

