#### NOTE:

• For participants with Grade 3 or 4 immune-related endocrinopathy where withhold of pembrolizumab is required, pembrolizumab may be resumed when AE resolves to ≤ Grade 2 and is controlled with hormonal replacement therapy or achieved metabolic control (in case of T1DM).

Pembrolizumab may be interrupted for situations other than treatment-related AEs such as medical / surgical events or logistical reasons not related to study therapy. Participants should be placed back on study therapy within 3 weeks of the scheduled interruption, unless otherwise discussed with the Overall PI. The reason for interruption should be documented in the patient's study record.

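### The second restart bullet in Section 6.2 allows both drugs to be restarted when toxicity has not resolved, a trigger on which the first bullet requires stopping; a stray *not* is the likeliest cause

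*Combined protocol and SAP*

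**What the plan says.** Restarting Study Interventions, in Section 6.2 of the combined protocol and SAP, has two bullets. The first reads: "If the toxicity does not resolve or the criteria for resuming treatment are not met, the participant must be discontinued from all study interventions". The second begins "If the toxicities do not resolve and conditions are aligned with what is defined in Table 7" and goes on to permit restart of both agents if the investigator so judges. It adds that in these cases, where the event is put down to the combination or to mirvetuximab soravtansine alone, "re-initiation of pembrolizumab as a monotherapy may be considered".

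The conditions for resuming are set elsewhere:

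- Table 7, instruction 2: "pembrolizumab can be resumed after AE has been reduced to Grade 1 or 0 and corticosteroid has been tapered". The same instruction says "Pembrolizumab should be permanently discontinued if AE does not resolve within 12 weeks of last dose".
- The note after Table 7, for Grade 3 or 4 immune-related endocrinopathies: "pembrolizumab may be resumed when AE resolves to ≤ Grade 2 and is controlled with hormonal replacement therapy", or once metabolic control is reached in type 1 diabetes.
- Table 4 (pneumonitis), note 2, uses the Grade 0 or 1 and taper condition for both drugs, and adds "Both agents should be permanently discontinued if AE does not resolve within 12 weeks of last dose".
- Section 6.3 lets dosing with both agents resume once the re-treatment criteria are met. If the event is attributed to one agent, "treatment with the second agent may resume provided all the other criteria are met".

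**The concern.** The two bullets share a trigger and give opposite orders. Non-resolution is sufficient for mandatory discontinuation under the first, and it is part of the condition for a permitted restart under the second. The second bullet also conflicts with its own qualifier, because Table 7 makes resumption depend on improvement to a stated grade.

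This is an operative safety instruction in a multi-centre trial of a checkpoint inhibitor. A site that follows the literal words could re-expose a patient who should stop. It could equally stop a patient whom Table 7 would allow to resume. The sentence on pembrolizumab monotherapy inherits the same faulty trigger, since it applies to the cases the second bullet describes.

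**Working it through.** The plan gives no figure here to reproduce, so the check is one of logic. Let R mean that the toxicity has resolved and C that the criteria for resuming are met. I assume that the first bullet's criteria for resuming are the Table 7 conditions named in the second.

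- First bullet: (not R) or (not C) → stop all study treatment.
- Second bullet as written: (not R) and C → may restart.
- Second bullet without *not*: R and C → may restart.

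| State | First bullet | Second bullet, as written | Second bullet, *not* removed |
|---|---|---|---|
| R, C | silent | silent | may restart |
| R, not C | stop | silent | silent |
| not R, C | stop | may restart | silent |
| not R, not C | stop | silent | silent |

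As written, the third state gets opposite orders, and the first state, which is the ordinary case for restarting, is covered by neither bullet. With *not* removed, the second bullet is the exact complement of the first: each of the four states gets one instruction.

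Whether the third state can occur depends on what resolution means, and the bullets do not say.

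1. *Resolution means reaching the level Table 7 requires.* Then C implies R, so the third state is empty. The second bullet never applies, and the ordinary restart case stays uncovered.
2. *Resolution means Grade 0.* A residual Grade 1 event with steroids tapered meets Table 7 but has not resolved. The first bullet stops the patient and the second permits restart.
3. *Resolution means Grade 0 or 1, applied to an endocrinopathy.* A Grade 3-4 event that has come down to Grade 2 and is controlled meets the Table 7 note but has not resolved. The bullets again conflict.

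On every reading the second bullet fails to authorise the ordinary case. It is either empty or contradictory.

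Removing *not* is not quite enough. Under reading 2, the first bullet would still stop the patient at Grade 1 with steroids tapered, whom Table 7 allows to resume. The meaning of resolution has to be fixed as well.

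**The case against.** The strongest reply is that the protocol's own usage favours reading 1. Table 4 speaks of symptoms resolving to Grade 1 or lower, Section 5.2.2 of toxicities resolved to Grade 2 or lower, and the Table 7 note of resolving to Grade 2 or lower. On that usage the second bullet is dead text, and no patient is told to do two things at once. This is fair and limits the harm. It does not rescue the bullet, which would then say nothing while appearing to say something about restarting after unresolved toxicity.

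A second reply is that restart rules exist elsewhere, so a site that follows Table 7 reaches the right answer for pembrolizumab. That also stands. A reader might infer that the protocol has no usable restart rule, or that it gives free licence to re-treat through unresolved toxicity. The documents support neither: the second bullet is tied to Table 7, the first bullet is mandatory, and Tables 4 and 7 carry 12-week stops. The cover is uneven, though. Table 7's resumption sentence and 12-week stop name pembrolizumab only; Table 4 names both agents, but only for pneumonitis. Section 6.3 relies on the general Grade 2 limit of Section 5.2.2, with stricter limits only for ocular events and pneumonitis.

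A third reply is that calling the *not* a slip is an inference. It is, but a strong one: removing it makes the bullets complementary and consistent with Table 7, and the same bullet contains two other typing errors (*bay be* and *if attributed*).

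**Conclusion.** The second bullet is wrong as written and should be corrected. It is a drafting error in a safety rule, not a flaw in the statistical design: type I error, power and sample size are unaffected, and no effect on endpoint counts is shown. Of four logical states, one is contradictory (or empty, if resolution means Table 7's level) and one is uncovered. These are rule states, not patients; the number of patients who might be affected cannot be computed from the documents. Practical harm is limited by Table 7, Table 4, Section 6.3 and the first bullet itself.

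The conclusion rests on taking the criteria for resuming to be those of Table 7. The diagnosis of a stray *not* is an inference; the conflict with the first bullet's trigger and with Table 7's requirement of improvement is on the face of the text.

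A reader might also infer that the first bullet should be softened to carry the Section 6.3 exceptions, namely resumption of the second agent by attribution and continuation after a delay of more than 12 weeks. The documents do not support writing those in here. The Attribution of Toxicity paragraph in Section 6.2 says attribution to one drug is likely to be difficult and requires both drugs to be held for Table 7 events whatever the attribution.

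**What to change.** Replace the condition in the second bullet with wording to this effect: *once the toxicity has come down to the level Table 7 sets for resuming (Grade 0 or 1 with corticosteroid tapered, or Grade 2 or lower for an endocrinopathy controlled as the Table 7 note describes), and the other Table 7 conditions hold, the investigator may restart both agents.* Keep the monotherapy sentence under that corrected condition, change *if attributed* to *is attributed* and *bay be* to *may be*. Use the same meaning of resolution in the first bullet, and otherwise leave that bullet as it is.

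Two separate, minor inconsistencies could go into the same amendment:

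- Study Calendar footnote d stops mirvetuximab soravtansine for any reported ocular symptom, whereas Table 3 continues dosing at Grade 1. The footnote points to the full protocol for detail, so it should be aligned with Table 3.
- The note under Table 6 allows a second dose reduction for a second event of Grade 3 or above, whereas Table 5 takes Grade 4 events off protocol therapy. The sponsor should state which governs. Changing the Table 6 note alone would not settle Grade 4 handling, since Table 7 continues pembrolizumab through Grade 4 hypothyroidism.

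The cost is one clarification amendment and a site memo. No procedures, patients or analyses are added.
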